8. PHARMACOKINETIC ANALYSIS

Pharmacokinetic samples were collected during the course of this study at baseline and before and during surgery. Additionally for patients undergoing ITI, PK samples were collected for the determination of IR and $t_{1/2}$ as applicable (further details are in Section 7.4.9).

PK activity data will be listed for the main study population and separately for measurements taken during the ITI period.

Activity measurements of the form “<x” (i.e., below the lower limit of quantification [LLOQ]) or “>x” (i.e., above the upper limit of quantification [ULOQ]) will be imputed as “x” in the calculation of PK parameters but displayed as “<x” or “>x” in the listings.

PK samples for Incremental recovery (IR) assessments are collected at the Baseline IR Visit, all interim visits and after a confirmed negative inhibitor in patients undergoing ITI.

IR is calculated using the following formula:

$$\text{IR (IU/dL per IU/kg)} = \frac{(\text{C}_{\text{max}} \text{ for FVIII activity} - \text{Pre-dose FVIII activity}) \text{ (IU/dL)}}{\text{Actual dose (IU/kg)}}$$

where:

- C_{max} (maximum concentration) is 30-minute FVIII activity post-dose
- FVIII activity <0.5 IU/dL was set to 0 IU/dL for calculation of IR.

IR data will be listed and summarized by visit in the FAS for exposure on the episodic and prophylactic treatment regimens.

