- l The rFVIII Fc PK assessments for half-life will be performed at 12-week intervals, only after IR determinations of ≥66% of expected value on 2 consecutive months. The first rFVIII Fc PK assessment will occur 12 weeks after IR≥66% of expected value is confirmed; subsequent PK assessments will be performed every 12 weeks thereafter for subjects who have not yet achieved the criteria for ITI complete success.
- m The subject's parent/caregiver must enter dosing information into the EPD **as soon as possible after an injection and within a maximum of 7 days following the injection** (Section 10.2.4.1.4). It is recommended that parents/caregivers enter dosing information immediately after an injection.
- n Injection site inspection is only to be performed if the subject receives an rFVIII Fc injection during a clinic visit.
- o For subjects who are receiving breast milk, maternal concomitant medications will also be collected at the same time points as other concomitant therapies, unless the breast milk is derived from a source other than the mother or the mother has not consented.

CONFIDENTIAL

The information contained herein may not be used, disclosed, or published without the written consent of Bioverativ Therapeutics Inc.

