#### 10.2.7.1. Assessment of Incremental Recovery and Half-Life During Immune Tolerance Induction Therapy

Upon the confirmation of a negative inhibitor titer, IR and  $t_{1/2}$  will be performed per the schedule of assessments (Section 4.2.2.3). Doses given for the purposes of full PK measurements (that is,  $t_{1/2}$ ), and IR will be calculated and recorded using the *actual* potency written on the vial as described in Section 10.1.1. IR and  $t_{1/2}$  assessments will be based on the one-stage clotting assay. The IR and  $t_{1/2}$  will be calculated by the Sponsor and provided to the PI.

For PK assessments, the subject must not be currently bleeding:

- Blood samples for recovery assessments will be taken predose (within 30 minutes prior to the start of the injection) and at 30 ( $\pm 5$ ) minutes after the start of a 50 IU/kg injection of rFVIII Fc. Subjects are required to have at least a 24-hour washout prior to the predose sample collection.
- For PK assessments to determine  $t_{1/2}$ , subjects must not have received an injection of rFVIII Fc within at least 72 hours of the predose sample collection. Sampling will occur at the following time points: predose and 30 ( $\pm 5$ ) minutes; 3 and 6 hours ( $\pm 10$  minutes); and 24 hours ( $\pm 60$  minutes), 48 hours ( $\pm 60$  minutes), and 72 hours

CONFIDENTIAL

The information contained herein may not be used, disclosed, or published without the written consent of Bioerativ Therapeutics Inc.

(±2 hours) after a 50 IU/kg injection of rFVIII Fc. Subjects should not have any additional doses of rFVIII Fc during the PK sampling period. If additional doses are required for clinical care, please immediately inform the Sponsor, as the  $t_{1/2}$  assessments must be repeated.

Whole blood will be drawn for exploratory assays related to immune response during ITI, starting with a sample collected at the pre-ITI assessment visit. A whole blood sample will be drawn every other month during ITI, at the time of the confirmation of complete success, partial success, or failure, and at the end of tapering (if applicable). Up to 10 mL of whole blood (minimum 3 mL) should be collected, as allowable by patient weight and institutional practice regarding blood draw restrictions for pediatric patients.

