### **16.3. Pharmacokinetics**

IR data will be listed and summarized by visit. For each subject, the observed IR estimated at each applicable visit will be averaged and summarized.

PK parameters, such as IR and  $t_{1/2}$ , derived from assessments during ITI will be listed for each applicable subject. PK parameters (IR and  $t_{1/2}$ ) for subjects undergoing ITI will be determined by real-time analyses of the FVIII activity data measured by the one-stage clotting assay to facilitate assessment of ITI outcome.

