2.2.4. Pharmacokinetic Endpoints

The only pharmacokinetic (PK) endpoint in this study is rFVIII Fc IR, as specified in Section [2.2.2](#).

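### Read literally, SAP section 8 sets below-limit FVIII activity to the limit when the ITI half-life is calculated; in a log-linear fit this can make a half-life under 6 h appear to meet the 6 h criterion

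*SAP*

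**What the plan says.** SAP section 8 replaces an activity reported as below the lower limit, "<x", by x: it "will be imputed as “x” in the calculation of PK parameters". The only different rule is for one parameter: "FVIII activity <0.5 IU/dL was set to 0 IU/dL for calculation of IR". The same section says that "for patients undergoing ITI, PK samples were collected for the determination of IR and" half-life. Protocol section 16.3 names both as PK parameters, which "derived from assessments during ITI will be listed for each applicable subject", and says that in ITI they are "determined by real-time analyses of the FVIII activity data measured by the one-stage clotting assay to facilitate assessment of ITI outcome". Protocol section 10.2.7.1 adds that they "will be calculated by the Sponsor and provided to the PI".

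The half-life profile (Protocol sections 4.2.2.4 and 10.2.7.1) is a 50 IU/kg dose with samples before the dose and at 0.5, 3, 6, 24, 48 and 72 h. During ITI it is done "only after IR determinations of ≥66% of expected value on 2 consecutive months", in subjects whose negative titer is confirmed. A half-life of at least 6 h is one of three criteria for complete success (Protocol 10.2.7.4.2, SAP 7.4.9). A half-life below 6 h is one relapse criterion, assessed 12 months after success.

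Neither document gives the assay limit, the half-life estimation method, the choice of points, the weighting or a fit-acceptance limit.

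**The concern.** A value set to the limit is higher than the true activity. Late in the profile this lifts the tail, flattens the slope of log activity on time and lengthens the half-life. The subjects most exposed are those with a half-life below 6 h, whom the criterion is meant to separate out, and the error runs towards success.

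Response to ITI is a secondary endpoint. By the time half-life is tested during ITI, titer and IR have already passed, so half-life decides. Under SAP 7.4.9 a subject with negative titers, adequate IR and a half-life under 6 h at 33 months is a partial success; an overstated half-life makes him a complete success. At month 12 a relapse shown only by half-life could be missed.

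**Working it through.** The plan has no half-life figure to reproduce, so this is an illustration under stated assumptions.

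**Inputs from the documents.** Dose 50 IU/kg; post-dose times 0.5, 3, 6, 24, 48, 72 h; IR 1.901 IU/dL per IU/kg for children under 6 years (Protocol Table 1); 66% of that is 0.66 × 1.901 = 1.255.

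**Assumed.** Limit of quantification (LLOQ) 0.1, 0.5 or 1.0 IU/dL (0.5 is the cut-off in the IR rule, 1 the severity cut-off for hemophilia A); a high individual IR of 2.5; mono-exponential decay; true half-life h of 3, 4, 5 or 5.5 h. That is 3 × 3 × 4 = 36 cases.

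**Formulas.** Activity C(t) = 50 × IR × 2^(−(t − 0.5)/h); values below the LLOQ are set to it; estimated half-life = ln 2 / (−slope) from unweighted least squares of ln C on t.

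**Which samples fall below the limit.** A sample at time t is below the limit when h < (t − 0.5) × ln 2 / ln(50 × IR / LLOQ). For t = 48, IR 1.901, LLOQ 0.5: 47.5 × 0.693 / ln 190.1 = 6.27 h. Over the grid the cut-off is 2.28–3.94 h for the 24 h sample, 4.62–7.95 h for 48 h and 6.95–11.97 h for 72 h. So with a half-life under 6 h the 72 h value is always below the limit. The 48 h value is always below it at LLOQ 0.5–1.0 with IR 1.255–1.901, and in 31 of the 36 cases overall.

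**One case in full** (IR 1.901, LLOQ 0.5, true 5 h). Activities are 95.05, 67.21, 44.34, 3.66, 0.13 and 0.005 IU/dL; the last two become 0.5. Mean time is 153.5/6 = 25.58 h, the sum of squares of time 4182.2, and the cross-product with ln C −333.3. The slope is −333.3/4182.2 = −0.0797 per hour, and the half-life 0.693/0.0797 = 8.70 h.

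**All six points kept**, estimated half-life (h) for true 3 / 4 / 5 / 5.5 h:

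| LLOQ (IU/dL) | IR 1.255 | IR 1.901 | IR 2.5 |
|---|---|---|---|
| 0.1 | 7.30 / 7.10 / 6.98 / 7.11 | 6.81 / 6.63 / 6.62 / 6.79 | 6.52 / 6.36 / 6.43 / 6.59 |
| 0.5 | 10.10 / 9.74 / 9.51 / 9.44 | 9.20 / 8.88 / 8.70 / 8.63 | 8.69 / 8.40 / 8.23 / 8.17 |
| 1.0 | 12.06 / 11.60 / 11.28 / 11.17 | 10.80 / 10.41 / 10.15 / 10.06 | 10.11 / 9.75 / 9.52 / 9.44 |

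**Other fits**, cases out of 36 estimated at 6 h or more:

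| Fit | Cases at ≥6 h |
|---|---|
| Log-linear, all six points | 36 |
| Log-linear, first below-limit point only | 20 |
| Nonlinear, 1/y² weights | 9 |
| Nonlinear, 1/y weights or unweighted | 0 |
| Log-linear, below-limit values excluded | 0 (true value recovered in all 36) |

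Choosing points by best adjusted R² does not help: it picks all six in every case.

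**With assay noise** (lognormal, 4000 runs per setting), the all-six fit passes a true 5.5 h in 100% of runs in all nine LLOQ × IR settings. A fit on the points before the first below-limit value passes it in about 0–3% (10% CV) or 2–17% (20% CV).

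**The case against.** The strongest reply is that the rule may never touch the half-life that is analysed. The Sponsor computes it in real time, and no passage ties that calculation to SAP section 8. SAP 7.4.9 lists half-life measurements without saying that they are re-derived. A narrower reading of section 8 is also possible: it gives a formula for IR alone, and SAP 2.2.4 says "The only pharmacokinetic (PK) endpoint in this study is rFVIII Fc IR". This stands in part. SAP 2.2.4 limits endpoints, whereas the rule is written for parameters, and Protocol 16.3 counts half-life among those. But whether the real-time value follows the SAP is unknown.

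Second, the rule alone does not produce the error; a fit that keeps imputed points is also needed. That stands: unweighted or 1/y-weighted nonlinear fits, or the usual terminal fit without below-limit values, give no false pass here. Some flattened fits might also be rejected on fit quality (adjusted R² is 0.64–0.89 at LLOQ 0.5–1.0 and IR 1.255–1.901), but no limit is stated.

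Third, few subjects are exposed, ITI response is descriptive, the listings still show "<x", and titer and IR also detect relapse. All true, and these bound the point.

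A reader might infer that the trial's half-life values are biased, or that subjects will be declared complete successes before 33 months. The documents support neither: they do not fix the method, and early declaration would require the real-time calculation to use the SAP rule.

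**Conclusion.** The point holds as a conditional one. The only written rule for below-limit activity that reaches half-life is unsuitable for it, and nothing else in the plan prevents the consequence. If it is applied in an unweighted log-linear fit with all points kept, a true 3–5.5 h reads as about 6.4–12.1 h over LLOQ 0.1–1.0 IU/dL and IR 1.255–2.5. The narrower 8.6–12.1 h belongs to LLOQ 0.5–1.0 and IR 1.255–1.901 and should not be quoted without those assumptions. The direction, towards meeting the 6 h criterion, does not depend on the assumed limit within this range, but it does depend on the fit.

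The possible harm is a partial success classed as complete, or a missed half-life relapse. It is confined to ITI subjects with negative titer, adequate IR and a short half-life, a number that the documents do not allow one to estimate. It is worth fixing because it bears on a secondary endpoint and the correction is small. Confidence is medium, because the link from SAP section 8 to the analysed half-life is not stated.

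**What to change.** Amend SAP section 8 as follows:

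- The rule replacing "<x" by x does not apply to half-life.
- Post-dose values below the limit are excluded from the terminal log-linear fit, or a censored-data fit is used.
- Half-life is reported as not evaluable when fewer than three quantifiable post-dose points remain.
- The LLOQ and the half-life method are stated.
- The Sponsor's real-time ITI calculation is stated to use the same rule.

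The cost is one SAP paragraph and one programming rule. There are real downsides. Some half-lives will come out shorter. With below-limit values excluded, assay noise makes a true 6.5 h read below 6 h in about 0–5% of runs at 10% CV and 3–20% at 20% CV. Some profiles may become non-evaluable: below a half-life of about 2.3–3.9 h, depending on LLOQ and IR, the 24 h sample is also below the limit. Only the 0.5, 3 and 6 h samples then remain, and one missed sample loses the estimate.

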9. SAFETY ANALYSIS

9.1. General Safety Principles

Safety analyses will be based on the Safety Analysis Set and unless otherwise specified, presented by the treatment regimen groups described in Section 5.1.1.1 .

9.2. Analysis of Primary Endpoint or specified safety endpoints

The primary safety endpoint is the occurrence of inhibitor development as determined from the Nijmegen-modified Bethesda assay. Analysis of the incidence of positive inhibitor formation is detailed in Section 9.4.3.

9.3. Adverse Events

An adverse event (AE) is any untoward medical occurrence in a patient or clinical investigation patient administered a pharmaceutical product and that does not necessarily have a causal relationship with this treatment. An AE can therefore be any unfavorable and unintended sign (including an abnormal laboratory finding), symptom, or disease temporally associated with the use of a medicinal (investigational) product, whether or not related to the medicinal (investigational) product.

Bleeding episodes in this patient population are not considered as AEs. Bleeding episodes that meet a serious criterion should be reported as serious adverse events (SAE). All bleeding episodes after the Baseline Visit will be captured in the EPD that the patient's parents/caregivers will be maintaining throughout the study period.

AEs will be classified using the Medical Dictionary for Regulatory Activities (MedDRA) system organ classes and preferred terms. MedDRA version 20.0 will be used in this study. All AEs will be listed.

The incidence of AEs will be summarized by system organ class (SOC) and preferred term (PT). Summaries will be included for all AEs as well as by severity and relationship to treatment. Patient listings will be provided for all AEs, SAEs, AEs resulting in discontinuation of study treatment and/or from the study, and deaths.

AEs that occurred during major surgical/rehabilitation periods will be included in the overall (top-line) summary of AEs but not in any of the other AE tables. Consideration is given to adverse events with an onset date at the start of the surgical/rehabilitation period in the event the pre-surgical dose was administered the day before the surgery.

All adverse event listings will include the onset and resolution study days relative to Study Day 1, which is the date of the first rFVIIIc treatment. AEs that are emergent prior to the first rFVIIIc treatment, AEs that are emergent during a major surgical/rehabilitation period, and AEs that are emergent on the day of surgery will be flagged. Similarly, AEs that are emergent after inhibitor development will be indicated separately as per the period during which they occurred.

Events of overdose will not be included in the AE summary tables unless they are determined to be AEs.

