#### **10.2.8.2.2. Major Surgery**

Major surgery will only be allowed in the study after the subject has had at least 3 injections of rFVIII Fc without safety concerns. If a subject needs to undergo major surgery prior to 3 injections, they will be withdrawn from the study. The Investigator must consult with Bioverativ in advance of the surgery.

All major surgeries must take place in a center that can provide study treatment, trained study personnel, postoperative assessments, and hematological consult by the Investigator or Sub-Investigator. If surgery does not take place in such a setting, the subject will be withdrawn from the study.

In addition, subjects who require major surgery may receive rFVIII Fc if:

1. The surgery occurs within the contracted institution for the study and/or a separate agreement has been executed, permitting the use of study drug and Bioverativ's rights to data generated in the study at an alternative institution deemed appropriate by the Principal Investigator or designee.
2. The Investigator and/or appropriate qualified/licensed delegate is available to:
  - a. Administer all rFVIII Fc doses required during surgery and during postoperative rehabilitation (if applicable).
  - b. Provide medical oversight and guidance throughout the duration of the preoperative and the intraoperative periods.

All major surgeries will be reported as SAEs, even if the surgery does not otherwise meet the definition of an SAE.

Samples for determination of predose FVIII activity levels and inhibitor formation will be collected prior to the dose of rFVIII Fc given for the surgery, and FVIII recovery levels will be sampled 30 ( $\pm$ 5) minutes after the start of the rFVIII Fc injection.

For major surgeries, a repeat blood draw for FVIII activity should be taken approximately 9 hours after the start of the injection, but may alternatively follow local standard of care for determining when the next dose of rFVIII Fc should be administered. While hospitalized, blood

CONFIDENTIAL

The information contained herein may not be used, disclosed, or published without the written consent of Bioverativ Therapeutics Inc.

will be drawn daily to be tested at the local laboratory for FVIII activity so that monitoring of the subject can occur in real time.

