#### **15.3.2. Serious Adverse Events**

Any SAE experienced by the subject between the time of signing the ICF and the Safety Follow-up Visit/Telephone Call is to be recorded on an SAE form, regardless of the severity of the event or its relationship to study treatment. SAEs must be reported to Quintiles Pharmacovigilance and the designated personnel within 24 hours as described in Section 15.3.3. Follow up information regarding an SAE must be reported within 24 hours.

Any SAE ongoing when the subject completes the study or discontinues from the study will be followed by the Investigator until the event has resolved, stabilized, or returned to baseline status.

In this study, the following events are considered medically important and must be reported as SAEs:

- A subject develops an inhibitor, as defined in Section 10.2.5.

CONFIDENTIAL

The information contained herein may not be used, disclosed, or published without the written consent of Bioerativ Therapeutics Inc.

- A subject develops a Grade 2 or greater allergic reaction in association with administration of rFVIII Fc defined as follows using the Recommendations for Grading of Acute and Subacute Toxic Effects on the WHO scale [[WHO Handbook 1979](#)]:
  - Grade 2: bronchospasm; no parenteral therapy needed
  - Grade 3: bronchospasm; parenteral therapy required
  - Grade 4: anaphylaxis
- A subject develops a vascular thrombotic event in association with the administration of rFVIII Fc, with the exception of IV injection site thrombophlebitis
- A subject undergoes major surgery

Allergic reactions, including anaphylaxis, have been reported with FVIII products. The subject's parents/caregivers (and the subject, if applicable) should be informed of early symptoms and signs of hypersensitivity reactions, including difficulty breathing, chest tightness, swelling of the face, rash, or hives. If such an event occurs while the subject is at home, the parents/caregivers should be instructed to seek immediate medical care for the subject.

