### **16.5. Safety**

Unless specified otherwise in the SAP, safety data will be summarized overall. Subjects developing a confirmed positive inhibitor test after exposure to rFVIII Fc study drug (the Inhibitor Subgroup) will have their safety data included up to the time of the last negative inhibitor test; safety data collected after the time of the last negative inhibitor test will be summarized separately.

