#### **16.5.1. Analysis Population**

The Safety Analysis Set is defined as all subjects who receive at least 1 dose of rFVIII Fc study drug. Safety analyses will be based on the Safety Analysis Set, including the data collected on or after the time of the first injection of rFVIII Fc.

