### **16.5.2.2. Adverse Events**

AEs will be coded using the Medical Dictionary for Regulatory Activities. The incidence of AEs will be summarized by system organ class and preferred term. Summaries will be for all AEs as well as by severity and relationship to treatment. Subject listings will be provided for all AEs, SAEs, AEs resulting in discontinuation of study treatment and/or from the study, and deaths. Unless otherwise specified in the study SAP, AEs and SAEs occurring during treatment with the ITI regimen will be summarized and listed separately.

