2. STUDY OBJECTIVES AND ENDPOINTS

2.1. Study Objectives

2.1.1. Primary Objective(s)

The primary objective of the study is to evaluate the safety of rFVIII Fc in previously untreated patients (PUPs) with severe hemophilia A.

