9.4.3.1. Endpoint Definition

A positive inhibitor occurs where a patient has a value ≥ 0.6 Bethesda Units (BU/mL) confirmed on re-testing at least 2 weeks later. See Section 5.1.2.4 for exact definition. Both tests must be performed by the central laboratory. Results from blood samples collected during surgical/rehabilitation periods for the purpose of determining the presence of an inhibitor will be included in this analysis. Inhibitor test data will be listed for all patients and separately for patients with positive inhibitors.

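### Adverse events in major surgical/rehabilitation periods are left out of every AE table except the top-line, so their tabulation by term, severity and relatedness is missing

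*SAP*

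**What the plan says.** - **The rule.** SAP 9.3: adverse events in major surgical/rehabilitation periods are "included in the overall (top-line) summary of AEs but not in any of the other AE tables".
- **What the top-line holds.** SAP 9.3.2: patient counts and percentages for TEAEs, related TEAEs, serious TEAEs, related serious TEAEs, discontinuations and deaths. It has no breakdown by term or severity.
- **Denominator.** SAP 5.3.2 bases adverse-event percentages on the Safety Analysis Set. Nothing is subtracted for surgical time.
- **Length of the period.** SAP 5.4.3: at its broadest, from the pre-surgery dose to just before the first regular prophylactic dose after postoperative care or rehabilitation.
- **What the Protocol asks for.** Section 16.5.1: "Safety analyses will be based on the Safety Analysis Set, including the data collected on or after the time of the first injection". Section 16.5.2.2: "Summaries will be for all AEs as well as by severity and relationship to treatment". Section 16.5 gives some latitude: "Unless specified otherwise in the SAP, safety data will be summarized overall".
- **Serious events.** Protocol 10.2.8.2.2: "All major surgeries will be reported as SAEs, even if the surgery does not otherwise meet the definition of an SAE". Protocol 15.3.2 also makes inhibitor development a mandatory SAE, together with thrombosis ("A subject develops a vascular thrombotic event in association with the administration of" the product). SAP 9.3.7 plans a summary of treatment-emergent SAEs by class and term for the study overall and mentions no exclusion.
- **Primary endpoint.** SAP 9.4.3.1: "Results from blood samples collected during surgical/rehabilitation periods for the purpose of determining the presence of an inhibitor will be included" in the inhibitor analysis.
- **Outputs and declared changes.** SAP Section 12 has a listing, but no summary table, of adverse events in surgical/rehabilitation periods. SAP Section 10 declares three differences from the Protocol, and this is not one of them.

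**The concern.** Safety is the purpose of the trial (SAP 2.1.1: "The primary objective of the study is to evaluate the safety of" the product in previously untreated patients). The rule takes events out of the numerators of the detailed tables and leaves the denominators alone, so the error runs in one direction.

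The excluded window matters for safety. Every major surgery produces a mandatory SAE. SAP 6.2.2.4 treats major surgery as a risk factor for inhibitor development, and the surgery schedule in Protocol 4.2.2.6 includes inhibitor tests at postoperative visits. SAP 9.3.10 plans no outputs for events of special interest and relies on medical review of the existing outputs. The class-and-term tables are thus the main tabulation in which a thrombotic or allergic event would be seen by name, and a surgical-period event would not be in them.

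**Working it through.** The plan states no figure for this point, so there is none to reproduce. The check is a comparison of texts followed by a bound.

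**1. Tables affected.** Read literally, the SAP 9.3 rule reaches the TEAE table by class and term, the descending-incidence tables, and the severity, relationship, SAE and discontinuation tables. Only the top-line table is spared.

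**2. Texts that conflict with the rule.**
- Protocol 16.5.2.2 wants every adverse event summarised, including by severity and relationship. The Protocol does set some safety data apart, namely data after the last negative inhibitor test (16.5) and ITI-regimen events (16.5.2.2), but each is still to be summarised separately. It has no such provision for surgical-period events, and its surgical-period exclusion in 16.2.2 concerns visit-based efficacy endpoints.
- The paragraph of SAP 9.3 just before the rule promises the same full summaries as the Protocol.
- SAP 9.3.7 describes the SAE table as an overall summary. It agrees with 9.3 only if the exclusion is read into it.
- The SAP 9.3 sentence on onset at the very start of the period says that such events receive consideration but gives no rule for assigning them.

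**3. Direction.** Patients are counted once per term (SAP 9.3.3). Removing events cannot add a patient to a term, so incidence by term stays the same or falls. In the severity and relationship tables a patient is counted at the highest grade or relationship (SAP 9.3.5, 9.3.6). Dropping a surgical-period event can therefore also move a patient to a lower row.

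**4. Size.** Inputs: N = 105, the planned number dosed (SAP 3.3), and s, the number of patients with major surgery, which is an assumption because the documents give none. If each mandatory surgery SAE has its onset inside the period and none of these patients has another SAE outside it, the SAE table omits

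maximum shortfall = s/105

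| s (assumed) | Maximum shortfall, percentage points |
|---|---|
| 1 | 1/105 = 0.95 |
| 3 | 3/105 = 2.9 |
| 5 | 5/105 = 4.8 |
| 10 | 10/105 = 9.5 |

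If a share p of these patients also has an SAE outside the period, the expected shortfall is s(1 − p)/105. With s = 5 and p assumed between 0.2 and 0.6:
- p = 0.2: 5 × 0.8 = 4 patients, 4/105 = 3.8 points
- p = 0.6: 5 × 0.4 = 2 patients, 2/105 = 1.9 points

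A preferred term seen only in these periods would show 0%, whatever s is.

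**5. Agreement between tables.** A patient whose only SAE is the major surgery is in the top-line SAE count and absent from the SAE table. For an inhibitor with onset in the period, the patient is in the primary numerator and the top-line count, but the mandatory inhibitor SAE is missing from the SAE table.

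**The case against.** The strongest case for the plan is that this is a matter of presentation. Four parts of it stand.

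- **Disclosure.** The top-line table keeps the patient counts set out in SAP 9.3.2, by regimen and inhibitor subgroup. Surgical-period events are flagged in the listings and have a listing of their own. A reader might infer that peri-operative thrombotic or inhibitor SAEs appear only in a listing. The documents do not support that: such events are in the top-line counts, and inhibitors are also tabulated in the primary and supporting analyses (SAP 9.4.3.2, 9.4.3.3).
- **Latitude.** Protocol 16.5 lets the SAP depart from an overall summary, and SAP Section 10 claims to list only major differences. The Protocol does not forbid separate treatment of surgical-period data, and the silence of Section 10 is by itself a documentation gap.
- **Consistency.** SAP 9.4 and 9.5 also keep laboratory values and vital signs from major surgical periods out of summaries while listing them. Part of any SAE shortfall would be the surgery itself, which is an SAE by reporting convention.
- **Scale.** Only major surgery triggers the rule. Port placement, minor dental extraction and abscess drainage are minor (Protocol 10.2.8.1). Few patients may be affected.

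It is also fair that the inhibitor analysis and the AE tables use different sources and denominators, so they need not match exactly even without the exclusion.

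The answer to the central point is that latitude to summarise separately does not cover leaving out the summary, and listings do not give incidence by term, severity and relatedness.

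**Conclusion.** The point holds in a limited form. No summary table gives surgical-period adverse events by term, severity or relatedness. The detailed tables can understate incidence and may disagree with the top-line table, and the rule conflicts with Protocol 16.5.2.2 and with other text in SAP 9.3 and 9.3.7.

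The size is at most 1/105, about 0.95 percentage points, per affected patient in an overall column. It is zero for a patient who has the same term, or for the SAE table another SAE, outside the period. The total depends on the number of major surgeries, which the documents do not give, so the 1 to 10 patients used in the check are illustrative. The bound assumes about 105 dosed patients and, for the surgery SAE, an onset inside the period.

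A reader might go further and infer that the primary endpoint is affected or that events vanish from the report. Neither follows: inhibitor results from these periods are retained in the primary analysis, and the events remain in the top-line counts and the listings. The change is still worth making because it alters reported safety results in a trial whose primary objective is safety.

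**What to change.** Delete the exclusion from SAP 9.3, so that all TEAEs and SAEs enter all AE tables. Add one table of events in major surgical/rehabilitation periods by system organ class and preferred term, with severity and relationship. SAP 6.5 already sets a precedent by presenting major protocol deviations from these periods separately within the summary. Replace the sentence on onset at the start of the period with a rule that can be programmed.

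If the sponsor keeps the exclusion, the parallel table is still needed, SAP 9.3 and 9.3.7 must be reconciled, and the departure should be listed in SAP Section 10.

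The cost is a wording change, one extra table and slightly less favourable reported incidences. No new data are needed.
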